## **4.2. Scientific Rationale for Study Design**

Nirmatrelvir/ritonavir FDC tablet is an alternative formulation for current commercial tablets to increase the adherence. The 4 different test formulations are designed to evaluate the effect of nirmatrelvir drug loading and disintegrant level on the performance of FDC tablets relative to the commercial product. The objective of the study is to estimate the rBA of nirmatrelvir/ritonavir of 4 different FDC tablets formulations (Test formulations) compared to the nirmatrelvir/ritonavir commercial tablets (Reference formulation) under fasted conditions. The study will also assess the safety and tolerability of nirmatrelvir/ritonavir oral FDC and commercial tablet formulations in healthy adult participants.

The study is being designed as a crossover study to account for any period effect. Between each treatment, a minimum of 4 days washout is proposed to minimize any residual nirmatrelvir and ritonavir concentrations prior to start of the next treatment, as nirmatrelvir has a half-life of approximately 6 to 13 hours when co-administered with ritonavir.

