### Rationale:

Nirmatrelvir is a potent and selective inhibitor of the SARS-CoV-2 Mpro that is currently being developed as an oral treatment of COVID-19. Ritonavir is a strong CYP3A4 inhibitor being used to inhibit the metabolism of nirmatrelvir in order to increase plasma concentrations of nirmatrelvir to values that are efficacious. The clinical development program for nirmatrelvir includes 12 completed clinical studies: 8 Phase 1 studies in healthy participants (C4671001, C4671008, C4671012, C4671013, C4671014, C4671015, C4671019 and C4671024), 1 Phase 1 study in renal impairment participants (C4671011), 1 Phase 1 study in hepatic impairment participants (C4671010) and 2 Phase 2/3 pivotal studies in COVID-19 patients (C4671005 and C4671006).

The 4 different test formulations are designed to evaluate the effect of nirmatrelvir drug loading and disintegrant level on the performance of FDC tablets relative to the commercial product. The purpose of this study is to estimate the rBA of nirmatrelvir/ritonavir of 4 different FDC tablet formulations relative to the commercial tablet formulation under fasted conditions in healthy adult participants.

CCI

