## Overall Design:

This is a Phase 1, open-label, single-dose, randomized, crossover study in healthy adult participants to estimate rBA of nirmatrelvir/ritonavir 300/100 mg of 4 different FDC Test formulations compared to the nirmatrelvir/ritonavir 300/100 mg commercial tablets (Reference formulation) under fasted conditions. The study will also assess the safety and tolerability of nirmatrelvir/ritonavir FDC and commercial tablet formulations in healthy adult participants. **CCI**

The study will consist of 5 treatments:

- Single oral dose of nirmatrelvir/ritonavir 300 (2 × 150)/100 mg commercial tablets (Treatment A)
- Single oral dose of nirmatrelvir/ritonavir 300/100 mg (2 × 150/50 mg) FDC tablets Test formulation 1 (Treatment B; nirmatrelvir/ritonavir 150/50 mg, low disintegrant),
- Single oral dose of nirmatrelvir/ritonavir 300/100 mg (2 × 150/50 mg) FDC tablets Test formulation 2 (Treatment C; nirmatrelvir/ritonavir 150/50 mg, high disintegrant)
- Single oral dose of nirmatrelvir/ritonavir 300/100 mg (2 × 150/50 mg) FDC tablets Test formulation 3 (Treatment D; nirmatrelvir/ritonavir 150/50 mg, high drug load).
- Single oral dose of nirmatrelvir/ritonavir 300/100 mg (3 × 100/33.3 mg) FDC tablets Test formulation 4 (Treatment E; nirmatrelvir/ritonavir 100/33.3 mg),

All treatments will be administered under fasted condition. Between each treatment, a minimum of 4 days washout is proposed to minimize any residual nirmatrelvir and ritonavir concentrations prior to start of the next treatment.

Approximately 15 healthy male and/or female participants will be enrolled and randomized to the study. Participants who discontinue from the study for non-safety reasons may be replaced at the sponsor's discretion in collaboration with the investigator.

Healthy participants will be screened to determine eligibility within 28 days prior to study treatment. Medical history and results of PEs, vital signs, 12-lead ECGs, and clinical laboratory evaluations will determine eligibility. Eligible participants will be admitted to the PCRU on Day -1 and will be confined in the PCRU until discharge on Day 4 of Period 4.

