### **Number of Participants:**

Approximately 15 healthy male and/or female participants will be enrolled and randomized to 1 of 5 possible treatment sequences to ensure at least 12 participants will complete the study.

Note: "Enrolled" means a participant's, or their legally authorized representative's, agreement to participate in a clinical study following completion of the informed consent process and randomization. A participant will be considered enrolled if the informed consent is not withdrawn prior to participating in any study activity. Potential participants who are screened for the purpose of determining eligibility for the study, but do not participate in the study, are not considered enrolled, unless otherwise specified by the protocol.

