## 4. STUDY DESIGN

### 4.1. Overall Design

This is a Phase 1, open-label, single-dose, randomized, crossover study in healthy adult participants to estimate rBA of 4 different nirmatrelvir/ritonavir 300/100 mg FDC tablets formulations (Test formulations) compared to the nirmatrelvir/ritonavir 300/100 mg commercial tablet formulation (Reference formulation) under fasted conditions. The study will also assess the safety and tolerability, of nirmatrelvir/ritonavir FDC and commercial tablet formulations in healthy adult participants. CCI [REDACTED]

Approximately 15 healthy male and/or female participants will be enrolled and randomized to 1 of 5 possible treatment sequences to ensure at least 12 participants will complete the study. Participants who discontinue from the study for non-safety reasons may be replaced at the sponsor's discretion in collaboration with the investigator. The replacement participant will receive the same treatment sequences as the participant who discontinued.

The study will consist of 5 treatments. Each enrolled participant will participate in 4 study periods to receive 4 different treatments according to the sequence determined by randomization:

- Treatment A: Single oral dose of nirmatrelvir/ritonavir 300 (2 × 150 )/100 mg commercial tablets under fasted conditions (Reference)

- Treatment B: Single oral dose of nirmatrelvir/ritonavir 300/100 mg (2 × 150/50 mg) FDC tablets Test formulation 1 (low disintegrant) under fasted conditions (Test 1)
- Treatment C: Single oral dose of nirmatrelvir/ritonavir 300/100 mg (2 × 150/50 mg) FDC tablets Test formulation 2 (high disintegrant) under fasted conditions (Test 2)
- Treatment D: Single oral dose of nirmatrelvir/ritonavir 300/100 mg (2 × 150/50 mg) FDC tablets Test formulation 3 (high drug loading) under fasted conditions (Test 3)
- Treatment E: Single oral dose of nirmatrelvir/ritonavir 300/100 mg (3 × 100/33.3 mg) FDC tablets Test formulation 4 under fasted conditions (Test 4)

Participants will be randomly assigned to 1 of 5 sequences as shown below in Table 1. Participants will be discharged on Day 4 of Period 4, following completion of all assessments. Between each treatment, a minimum of 4 days washout is proposed to minimize any residual nirmatrelvir and ritonavir concentrations prior to start of the next treatment. The total planned duration of participation from the Screening visit to the last follow-up phone call, is approximately 12 weeks.

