## 8. STATISTICAL METHODOLOGY AND STATISTICAL ANALYSES

### 8.1. Statistical Methods

### 8.2. Statistical Analyses

*For the primary objective, natural log transformed  $AUC_{inf}$  (if data permits),  $AUC_{last}$  and  $C_{max}$  for nirmatrelvir and ritonavir will be analyzed using a mixed effect model with sequence, period and treatment as fixed effects and participant within sequence as a random effect. Estimates of the adjusted mean differences (Test-Reference) and corresponding 90% confidence intervals will be obtained from the model. The adjusted mean differences and 90% confidence intervals for the differences will be exponentiated to provide estimates of the ratio of adjusted geometric means (Test/Reference) and 90% confidence intervals for the ratios. Treatment A will be the Reference treatment while Treatments B, C, D and E will be the Test treatments.*

*PK parameters, including plasma  $AUC_{inf}$  (if data permits),  $AUC_{last}$ ,  $C_{max}$ , **CCI** (if data permits) of nirmatrelvir and ritonavir will be summarized descriptively by analyte and treatment. Box and whisker plots for  $AUC_{inf}$  (if data permits),  $AUC_{last}$ , and  $C_{max}$ , will be plotted by treatment.*

Residuals from the model will be examined for normality and the presence of outliers via visual inspection of plots of residuals vs predicted values and normal probability plots of residuals but these will not be included in the clinical study report. If there are major deviations from normality or outliers then the effect of these on the conclusions will be investigated through alternative transformations and/or analyses excluding outliers. Justification for any alternative to the planned analysis will be given in the report of the study.

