## 10. APPENDICES

### Appendix 1. SAS CODE FOR ANALYSES

- An example of the PROC MIXED code is provided below:

```
proc mixed data=tab.pk;
  class seq period trt subject;
  model l&var= seq period trt / ddfm=KR;
  random subject(seq) / subject = subject(seq);
  lsmeans trt;
  estimate 'B vs A' trt -1 1 0 0 0;
  estimate 'C vs A' trt -1 0 1 0 0;
  estimate 'D vs A' trt -1 0 0 1 0;
  estimate 'E vs A' trt -1 0 0 0 1;
  ods 'Estimates' out=est&var;
  ods 'lsmeans' out=ls&var;
  ods 'covparms' out = cov&var;
  ods 'tests3'    out = tst&var;
run;
```

/\* Letter assignments for treatments (trt) within the estimate statement above are as follows;

A= Single oral dose of nirmatrelvir/ritonavir 300 (2 × 150)/100 mg commercial tablets under fasted conditions (Reference)

B = Single oral dose of nirmatrelvir/ritonavir 300/100 mg (2 × 150/50 mg) FDC tablets Test formulation 1 (low disintegrant) under fasted conditions (Test 1)

C = Single oral dose of nirmatrelvir/ritonavir 300/100 mg (2 × 150/50 mg) FDC tablets Test formulation 2 (high disintegrant) under fasted conditions (Test 2)

D = Single oral dose of nirmatrelvir/ritonavir 300/100 mg (2 × 150/50 mg) FDC tablets Test formulation 3 (high drug loading) under fasted conditions (Test 3)

E = Single oral dose of nirmatrelvir/ritonavir 300/100 mg (3 × 100/33.3 mg) FDC tablets Test formulation 4 under fasted conditions (Test 4) \*/;

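### Does the plan need its own confidence interval for high versus low disintegrant (C/B)?

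*Protocol*

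**What the plan says.** Protocol 4.2 states: "The 4 different test formulations are designed to evaluate the effect of nirmatrelvir drug loading and disintegrant level on the performance of FDC tablets". The sentence ends by naming the commercial product as the comparator. The synopsis rationale repeats this. In 4.2 the next sentence states the objective: relative bioavailability of the four test formulations against the commercial tablets, fasted.

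B and C share the 150/50 mg strength. B is labelled low disintegrant, and the synopsis lists C as "Treatment C; nirmatrelvir/ritonavir 150/50 mg, high disintegrant".

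The four primary objectives (Protocol section 3, SAP 2.2.1) each compare one test formulation with A, and the primary endpoint is the set of test/reference ratios. SAP 8.2, like Protocol 9.3.2, fixes the comparisons: "Treatment A will be the Reference treatment while Treatments B, C, D and E will be the Test treatments". The example code in SAP Appendix 1 has four ESTIMATE statements, all against A, the last being "estimate 'E vs A' trt -1 0 0 0 1". Its LSMEANS statement requests no differences. Protocol 9.1 and SAP 4.1 and 4.2 state that there are no hypotheses and no decision rules.

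**The concern.** The rationale names disintegrant level as one of two factors that the tablets were made to study. B and C look like the matched pair for it. The effect of disintegrant on performance relative to A is (C/A)/(B/A), which is C/B, yet no readable text plans a confidence interval for that ratio.

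Two separate intervals against A do not supply it by inspection. The estimates share A and many of the same participants, so they are correlated. In a study whose only product is estimates with intervals, the report might then be silent on how precisely a twice-mentioned formulation factor was estimated.

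**Working it through.** **1. What the plan sets out to estimate.** Set side by side, the objectives, the endpoint, the model text and the code all give B, C, D and E against A. The rationale sentence ends with the commercial product as comparator, and the objective that follows it in 4.2 uses the same comparator. No planned item lacks an analysis.

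**2. The plan's own precision figures (Protocol 9.5).** Inputs: within-participant SDs 0.1752 and 0.1378 (nirmatrelvir lnAUCinf, lnCmax), 0.2424 and 0.3282 (ritonavir); 15 participants; 90% intervals; 80% coverage probability. Residual df = 60 − 15 − 3 − 4 = 38.

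Half-width = t(0.95, 38) × SD × √(2/15) × √(χ²₀.₈₀(38)/38) = 1.6860 × SD × 0.3651 × 1.0891.

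This gives 0.1175, 0.0924, 0.1625 and 0.2201, the four stated values.

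**3. Variance of C − B in the actual design (Protocol Table 1).** Each participant receives 4 of the 5 treatments, so each treatment is taken by 12 participants and each pair of treatments by 9. B and C occur together in sequences 1, 2 and 5. Every treatment appears once in every period, so the period adjustment costs nothing.

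- Efficiency = (9 × 5)/(12 × 4) = 15/16.
- Variance of any treatment difference = 2/(12 × 15/16) × SD² = 0.1778 × SD².

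All ten pairwise differences, C − B included, have this same variance. A mixed model with fixed sequence and random participant gives the same figure for between- to within-participant variance ratios from 0.5 to 10.

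**4. Half-widths for ln(C/B), which are also those for each planned contrast with A.** Half-width at the assumed SD = 1.6860 × SD × √0.1778; the 80% coverage column multiplies this by 1.0891.

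| Parameter | SD | At assumed SD | 80% coverage | Limits around a ratio of 1, at assumed SD |
|---|---|---|---|---|
| Nirmatrelvir AUCinf | 0.1752 | 0.1245 | 0.1356 | 0.883 to 1.133 |
| Nirmatrelvir Cmax | 0.1378 | 0.0980 | 0.1067 | 0.907 to 1.103 |
| Ritonavir AUCinf | 0.2424 | 0.1723 | 0.1877 | 0.842 to 1.188 |
| Ritonavir Cmax | 0.3282 | 0.2333 | 0.2541 | 0.792 to 1.263 |

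These exceed the protocol's figures by √(0.1778/0.1333) = 1.155, because 9.5 uses 2/15 as if all 15 participants took both treatments. That is a separate matter. It affects the contrasts with A and C/B alike.

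With complete data a reader can therefore divide the two planned ratios to get C/B and attach the log-scale half-width of any planned contrast.

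**5. Incomplete data.** The protocol enrols 15 "to ensure at least 12 participants will complete the study". Take three dropouts from any sequences, each contributing 0, 1, 2 or 3 periods, with nobody replaced. That is 5 × 4 = 20 types taken three at a time with repetition: 20 × 21 × 22/6 = 1540 patterns, residual df 29 to 35.

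- SE(C − B)/SE(B − A): 0.890 to 1.173.
- SE(C − B)/SE(C − A): 0.875 to 1.124.
- Both ratios pooled, patterns counted equally: median 0.997; about 81% within 5% of 1, about 98% within 10%, about 1% above 1.10.
- The maximum of 1.173 needs all three Sequence 1 participants to leave after Period 2. If the three dropouts come from three different sequences, the maximum is 1.12.

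**The case for a change.** The best opposing argument is that intervals are what this study delivers, and the one for C/B costs a single line of code. Combining the two planned intervals as if independent would give 0.1761 for nirmatrelvir AUCinf instead of 0.1245, about 41% too wide (0.1761/0.1245 = 1.414). Replacement of dropouts is optional, PK data may be excluded under SAP 5.7 and 7.3, and the covariances needed for an exact interval are not in the planned output. Prespecification would also forestall a selective choice of test-versus-test comparisons in an open-label study that permits data reviews.

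The arithmetic stands, and so does the observation that no readable text plans this interval. It does not make the plan deficient:

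- The missing interval belongs to a quantity that is not among the readable objectives, and nothing in the plan turns on it.
- The 41% error comes from a wrong calculation by the reader. Borrowing a planned half-width is exact with complete data and usually close without.
- The Appendix 1 code is introduced as an example. Its ESTIMATE lines do not even request the confidence limits that SAP 8.2 promises for the contrasts with A, so it is no full list of the output.
- Reading C/B as a pure disintegrant effect assumes that the two tablets differ in nothing else. The documents give labels, not compositions.
- For drug load, the other named factor, the documents identify no matched comparator for D, so a C/B line would cover only half of the sentence it is meant to serve.

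**Conclusion.** The concern does not hold. The plan asks how each test formulation compares with the commercial tablets, and its objectives, endpoint, model and example code answer that question consistently. Leaving out C/B biases none of those estimates and changes no planned decision.

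What is absent is one printed interval for a quantity outside the readable objectives. With 15 completers its width equals that of every planned contrast. At 12 completers its standard error is 0.875 to 1.173 times that of the B or C contrast with A, and typically within 5%. Adding it as a supportive estimate is a matter of preference.

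This rests on the protocol's SDs for the absolute widths, on counting dropout patterns equally (a description of the range, not a forecast), and on the readable text. Several objectives and the end of SAP 8.2 are redacted, so a comparison between test formulations may already be planned there.

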### **4.2.1. Choice of Contraception/Barrier Requirements**

Human reproductive safety data are limited for nirmatrelvir, but there is no suspicion of human teratogenicity based on the intended pharmacology of the compound. Therefore, the use of a highly effective method of contraception is required (see [Appendix 4](#)).

### **4.2.2. Collection of Retained Research Samples**

Retained Research Samples will be collected and stored for further analyses which may, for example, provide greater understanding of the study intervention.

## **4.3. Justification for Dose**

The dose of nirmatrelvir/ritonavir 300/100 mg BID for 5 days is the approved therapeutic dose and treatment duration under emergency use authorization. This dose is lower than the highest dose evaluated in the Phase 1 C4671001 study and is safe and well-tolerated.

This study is designed to evaluate rBA of nirmatrelvir/ritonavir of 4 different FDC tablets formulations compared to nirmatrelvir/ritonavir commercial tablets in healthy adult participants at the approved therapeutic dose. Therefore, a single oral dose nirmatrelvir/ritonavir 300/100 mg will be used in this relative bioavailability study.

#### **4.4. End of Study Definition**

The end of the study is defined as the date of the last scheduled procedure shown in the [SoA](#) for the last participant in the trial.

A participant is considered to have completed the study if they have completed all parts of the study, including the last scheduled procedure shown in the [SoA](#).

### **5. STUDY POPULATION**

This study can fulfill its objectives only if appropriate participants are enrolled, including participants across diverse and representative racial and ethnic backgrounds. Use of a prescreening tool is utilized for study recruitment purposes, it will include collection of information that reflects the enrollment of a diverse participant population including, where permitted under local regulations, age, sex, and race, and ethnicity. The following eligibility criteria are designed to select participants for whom participation in the study is considered appropriate. All relevant medical and nonmedical conditions should be taken into consideration when deciding whether a particular participant is suitable for this protocol.

Prospective approval of protocol deviations to recruitment and enrollment criteria, also known as protocol waivers or exemptions, is not permitted.

#### **5.1. Inclusion Criteria**

Participants are eligible to be included in the study only if all of the following criteria apply:

##### **Age and Sex:**

1. Male and/or female participants must be  $\geq 18$  years of age, inclusive, at the time of signing the ICD.
  - Refer to [Appendix 4](#) for reproductive criteria for male ([Section 10.4.1](#)) and female ([Section 10.4.2](#)) participants.

##### **Type of Participant and Disease Characteristics:**

2. Male and female participants who are overtly healthy as determined by medical evaluation including medical history, PE, laboratory tests, vital signs and standard 12-lead ECGs.
3. Participants who are willing and able to comply with all scheduled visits, treatment plan, laboratory tests, lifestyle considerations, and other study procedures.
4. Female participants of childbearing potential must have a negative pregnancy test at screening.

**Weight:**

5. BMI of 17.5 to 30.5 kg/m^2; and a total body weight >50 kg (110 lb).

**Informed Consent:** .

6. Capable of giving signed informed consent as described in [Appendix 1](#), which includes compliance with the requirements and restrictions listed in the ICD and in this protocol.

**5.2. Exclusion Criteria**

Participants are excluded from the study if any of the following criteria apply:

**Medical Conditions:**

1. Positive test result for SARS-CoV-2 infection on Day -1.
2. Evidence or history of clinically significant hematological, renal, endocrine, pulmonary, gastrointestinal, cardiovascular, hepatic, psychiatric, neurological, or allergic disease (including drug allergies, but excluding untreated, asymptomatic, seasonal allergies at the time of dosing).
3. Clinically relevant abnormalities requiring treatment (eg, acute myocardial infarction, unstable ischemic conditions, evidence of ventricular dysfunction, serious tachy- or brady-arrhythmias) or indicating serious underlying heart disease (eg, prolonged PR interval, cardiomyopathy, heart failure greater than NYHA 1, underlying structural heart disease, Wolff Parkinson-White syndrome).
4. Any condition possibly affecting drug absorption (eg, gastrectomy, cholecystectomy).
5. History of HIV infection, hepatitis B, or hepatitis C; positive testing for HIV, HBsAg, HBcAb or HCVAb. Hepatitis B vaccination is allowed.
6. Other medical or psychiatric condition including recent (within the past year) or active suicidal ideation/behavior or laboratory abnormality or other conditions or situations related to COVID-19 pandemic (eg, contact with positive case) that may increase the risk of study participation or, in the investigator's judgment, make the participant inappropriate for the study.

### **Prior/Concomitant Therapy:**

7. Use of prescription or nonprescription drugs and dietary and herbal supplements within 7 days or 5 half-lives (whichever is longer) prior to the first dose of study intervention. Refer to [Section 6.9 Prior and Concomitant Therapy](#) for additional details.
  - Concomitant use of any medications or substances that are strong inducers of CYP3A4 are prohibited within 28 days prior to first dose of nirmatrelvir/ritonavir and during study treatment.
  - Concomitant use of any medications or substances that are inhibitors of CYP3A4 are prohibited during study treatment and 4 days after the last dose of study intervention.
8. Current use of any prohibited concomitant medication(s) or participant unwilling/unable to use a permitted concomitant medication(s). Refer to [Section 6.9 Prior and Concomitant Therapy](#).
9. Participants who have received a COVID-19 vaccine within 7 days before screening or admission, or who are to be vaccinated with a COVID-19 vaccine at any time during the study confinement period.

